1.6 Rationale for the Study

There remains significant unmet medical need for the treatment of active musculoskeletal disease in SLE that is refractory to treatment with NSAIDS and anti-malarial agents and necessitates the addition of corticosteroids, immunosuppressive medications and/or narcotic analgesia. A double-blind, randomized, placebo-controlled design will be used to reduce bias in assessment of safety, tolerability, and efficacy of JBT-101 in SLE subjects with active musculoskeletal disease. JBT-101 and placebo will be administered in addition to current standard of care that the subject is receiving, to reduce risk of precipitating disease flares by stopping standard-of-care treatments. There is limited metabolism of JBT-101, and JBT-101 has no impact on multiple cytochrome P450 systems, an observation that reduces the likelihood of adverse drug-drug actions in SLE patients on complex treatment programs.

The hypothesis is that JBT-101 will provide clinical efficacy in SLE patients with at least moderate musculoskeletal disease activity by activation of pathways that resolve ongoing, adverse immune responses and inhibit inflammatory cytokine production associated with SLE. JBT-101 is expected to decrease production of pro-inflammatory cytokines implicated in the pathogenesis of SLE, such as IFN α , IL-6, and IL-1 β . Further, JBT-101 is expected to activate apoptosis in activated immune cells and induce clearance of apoptotic cells (efferocytosis) and cellular debris by non-inflammatory macrophages. Through these mechanisms, JBT-101 is expected to provide efficacy in active musculoskeletal inflammation in SLE, without immunosuppression.

For the primary efficacy analysis, inflammatory pain will be measured daily using the maximum pain numerical rating scale (NRS), and longitudinal changes will be evaluated after 12 weeks (end of treatment). Other efficacy outcomes include categorical change in pain (improvement, no change, worsening), the number (%) of subjects achieving a 30% (or 50%, 75% or 100%) reduction in maximum pain from baseline to end of treatment, and SLE disease activity measures, including number of tender and swollen joints on 66/68 joint count, presence versus absence of arthritis by Safety of Estrogen in Lupus: National Assessment (SELENA) SLEDAI and score in the musculoskeletal domain of the British Isles Lupus Activity Group (BILAG) 2004, the SLE Responder Index and its domains (SELENA SLEDAI assessment, BILAG 2004 assessment, and Physician's Global Assessment), and disease flares. Efficacy also will be assessed with patient-reported outcomes [Lupus Activity Patient Global Assessment and Patient-Reported Outcomes Measurement Information

System (PROMIS)-29 Short Form, PROMIS Item Bank v2.0 - Cognitive Function test, and Treatment Satisfaction Survey]. Changes from baseline in secondary efficacy outcomes are expected to occur and be in the direction of improvement, although the changes are not expected to reach statistical significance at p < 0.05 after 84 days exposure in this first trial in relatively small numbers of SLE patients. In contrast, changes in the metabolipidomic profile and stimulated whole blood cytokine expression are expected within days, and changes in biomarkers of inflammation, such as C-reactive protein (CRP) and type I IFN gene expression, are expected to happen within a few weeks.

Safety assessments include patient-reported AEs, vital signs, physical examinations, complete blood count (CBC) with cell differential, metabolic panel, urinalysis, and 12-lead ECGs for QT/QTc intervals. Blood for JBT-101 concentrations and metabolites, biomarkers of inflammation, metabolipidomic profiles, cytokine expression in serum and stimulated whole blood, and analysis of type 1 IFN gene expression will also be collected. Confirmation of the lack of psychotropic properties of oral JBT-101 will be done using the Addiction Research Center Inventory-Marijuana (ARCI-M) questionnaire.

The mechanism of action of JBT-101 will be evaluated by measuring metabolipidomic profiles, to determine whether JBT-101 increases SPMs, especially lipoxin A4, and antiinflammatory eicosanoids, both in absolute amounts and relative to pro-inflammatory eicosanoid mediators. The downstream consequences of this activity on biologic pathways relevant to disease pathology in SLE will be tested, looking for decreased expression of cytokines and gene transcripts that are elevated during inflammation in SLE.

This is a first-in-SLE study of JBT-101. The data from this study will provide information on whether the benefit: risk profile in SLE supports further clinical development and progression to future pivotal clinical testing. The data will support selection of optimal dose and dose regimen of JBT-101 in future SLE studies.

1.6.1 **Rationale for the Inclusion and Exclusion Criteria**

The target population is adults with SLE who have active musculoskeletal disease (arthritis or tendonitis) with significant inflammatory pain, despite treatment with an anti-malarial drug unless intolerant of an anti-malarial drug, and who are on stable doses of prednisone $\leq 10 \text{ mg}$ daily or equivalent for at least 14 days prior to dosing with study product. To reduce risk to subjects in this first-in-SLE study, subjects will be excluded who have severe organ damage, severe disease activity and/or require > 10 mg day oral prednisone or equivalent for treatment. Additionally, patients with a recent or current history of substance abuse or those with chronic pain requiring narcotic analgesia will be excluded in order to limit confounding effects of these substances on our endpoints. Subjects will be ≥ 18 and ≤ 70 years of age at the time of signing the Informed Consent Form. Adults are selected as the target population, because neither toxicology studies in juvenile animals nor safety or efficacy assessments in children with SLE have been done yet.

Subjects with fibromyalgia are not excluded from the study. Given that up to about one-third of SLE patients have concomitant fibromyalgia, exclusion of SLE subjects with fibromyalgia

from this study is impractical and would delay and jeopardize completion of study enrollment. Multiple steps have been included in the trial design to account for the potential impact of pain from fibromyalgia on study results. To ensure that a significant component of the subjects daily pain NRS score is from inflammatory pain from joint/tendon involvements, subjects will be required to have arthritis and/or tendonitis on SELENA SLEDAI assessment or B score in the musculoskeletal domain of the BILAG 2004 assessment. The presence or absence of fibromyalgia and its severity will be assessed using the Fibromyalgia Symptom Score [107]. The absence versus presence of fibromyalgia (Fibromyalgia Symptom Score < 13 versus \geq 13 at Screening) will be used as a stratification variable at randomization and in subset analyses of the efficacy outcomes.

1.6.2 **Rationale for the Treatment Arm**

The JBT-101 doses selected for this study are within the range of doses that were well tolerated in previous Phase 1 and 2 studies and in a recently completed clinical trial in SSc, all sponsored by Corbus Pharmaceuticals Holdings, Inc. The JBT-101 oral doses selected for this study are 5 mg b.i.d., 20 mg q.d., and 20 mg b.i.d. Parallel dose assignment to JBT-101 in doses up to 20 mg b.i.d. is supported by a previous multiple ascending dose study and a Phase 2 study in humans in which JBT-101 doses up to 40 mg b.i.d. showed acceptable safety profiles and were well-tolerated. In a recently completed study of JBT-101 in systemic sclerosis and ongoing studies in dermatomyositis and cystic fibrosis (sponsored by Corbus) using similar doses to those proposed in this clinical trial (5 mg-40 mg daily), JBT-101 has been well tolerated with no severe AEs attributable to JBT-101. Each dose is expected have an acceptable safety profile, be well-tolerated, and provide clinical benefit, based on previous animal or human testing and the nature of the inflammatory components of SLE. Based on preclinical data and early higher dose clinical data, it is expected that any safety risk and clinical efficacy of JBT-101 in humans will be related to exposure. Based on extrapolation from animal models of inflammation, 5 mg q.d. was estimated to be about the median dose required for efficacy in humans. However, information from the cystic fibrosis study and from a cutaneous model of E. coli- induced inflammation [101] suggests that 5 mg b.i.d. may be more effective than the 5 mg q.d. dose:

- The 5 mg q.d. dose has some but more limited effects than 20 mg b.i.d. on biomarkers in the sputum in cystic fibrosis patients, with biologic effects of 20 mg b.i.d. ≥ 20 mg q.d. and > 5 mg q.d. doses
- In a human model of innate immune responses (E. coli- induced cutaneous inflammation) the 5 mg b.i.d. dosing demonstrates the expected mechanism of action by enhancing resolution of inflammation. Some activities such as induction of Specialized Pro-resolving lipid Mediators are less with 5 mg b.i.d. than with 20 mg b.i.d. whereas other activities such as inhibition of neutrophil infiltration in the skin are equal

Since the 5 mg b.i.d. dose does not pose any safety issues, we plan to use 5 mg b.i.d. as the low dose arm. The JBT-101 20 mg dose is expected to provide maximal or near maximal levels of clinical benefit, and the JBT-101 20 mg b.i.d. dose is expected to provide maximal/plateau levels of clinical benefit. Inclusion of the JBT-101 20 mg q.d. and 20 mg

b.i.d. doses is expected to maximize opportunity to detect clinical efficacy, safety signals, evidence of biologic activity, and effects on biomarkers in this study. Finally, the availability of data from three different doses of JBT-101 will facilitate the exploratory modeling of relationships between plasma concentrations of JBT-101 and efficacy outcomes, SAEs, biomarkers of inflammation, and levels of certain SPMs.

The 84 days duration of dosing is supported by findings in 13-week toxicology studies in rats and dogs. This study will provide data on safety, tolerability, plasma concentrations, and clinical efficacy of JBT-101 over a longer exposure than in a shorter study.

In support of oral administration q.d. or b.i.d. without regard to fed/fasted state, JBT-101 is well absorbed from the gastrointestinal tract and exhibits dose proportional PK at the doses to be tested in this study. Based on PK results in previous clinical trials, Tmax is expected to be between 2.7 to 3.5 hours for the 5 and 20 mg doses in the current trial, which supports the timing of 3 hours post dosing as an estimate of time of maximal plasma concentrations. The average terminal chemical half-life of JBT-101 in subjects who received 10 mg or 20 mg q.d. in previous studies ranges from 3.7 to 4.4 hours and the biologic effects of JBT-101 are longer, which supports q.d. and b.i.d. testing. Doses to be tested in this study have not shown a significant food effect in a prior clinical study, which supports dosing without regard to fed state.

1.6.3 **Rationale for the Control Arm**

Inclusion of a placebo cohort in this study is important to control for variations in disease activity and AEs that occur commonly in SLE as a result of their disease, co-morbid illness and/or adverse effects of prescribed medications. Because of the relatively short duration of the study and maintenance of the subject's existing medications for musculoskeletal disease activity and pain, the inclusion of a placebo cohort does not impose undue risk on these subjects. To limit risk of increasing disease activity in a placebo-controlled trial, patients with a BILAG A in any organ system at Screening or Visit 1 (Day 1) will be excluded, because those individuals should receive a new treatment for that severely active organ system. Subjects will be maintained on their SLE medications from Screening throughout Visit 6 (Day 113), to reduce a risk of disease flare precipitated by discontinuation of medications to meet entry criteria. Stopping rules will limit the risk of AEs due to severe increases in disease activity.

1.6.4 **Rationale for Mechanistic Studies**

The rationale for the mechanistic studies is to validate the preclinical studies and investigate the *in vivo* effects of JBT-101 on pathways that promote ongoing inflammatory responses and those that promote resolution of inflammation. Pre-clinical studies done *in vitro* using healthy control and SLE PBMC and in animal models suggest that the drug's antiinflammatory properties are mediated by inhibition of pro-inflammatory cytokines such as IL-1 β , IL-6, IFN α and IFN γ and by increased production of prostaglandins and other bioactive lipids that facilitate the resolution of inflammation. All of these cytokines have been implicated in the pro-inflammatory milieu that is associated with SLE. Additionally, although JBT-101 has not been demonstrated previously to have an effect on TNF α we plan to verify this in the planned mechanistic studies, which will be completed using stored specimens should the clinical results warrant further study. In addition to supplying more information that will enhance our understanding of the mechanism of action, it is possible that the mechanistic studies will identify a surrogate biomarker for response that is more sensitive and specific than currently accepted disease activity measures. This has significant potential importance for the design of a Phase III study.

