As of July 2017, a number of the AEs associated with CB1/CB2 agonists have been reported in subjects exposed to JBT-101 and future subjects are at risk for these same AEs. As seen in pooled safety data from the 2 Phase 1 studies and 2 Phase 2 completed clinical trials, AEs that occurred in \geq 5% of JBT-101 treated subjects were fatigue, dry mouth, arthralgias, dizziness, nausea and vomiting. Many of the other AEs listed as class effects of CB1/CB2 agonists have been reported by JBT-101-treated subjects, albeit at frequencies lower than 5% as of July 2017 (see Tables 17, 18 and 20 in the Investigator Brochure for JBT-101). JBT-101 is a full agonist of CB2, with little evidence of psychotropic activity at likely therapeutic doses, because of limited ability to cross the blood-brain barrier and reduced affinity for CB1. Psychotropic activity of JBT-101 will be tested formally with the ARCI-M questionnaire [106].

Prolongations of QTc interval to less than 500 msec total and up to 39 msec prolongation from pre-treatment baseline were observed in a previous Phase 1 study, and all of these prolongations were judged not clinically significant. They were observed in some subjects \geq 65 years of age exposed to JBT-101 at a total daily dose greater than or equal to 180 mg for seven days. The QTc changes were also observed on ECGs not done using standard techniques to measure QT/QTc intervals. For this reason, to ensure safety of subjects, the QT/QTc interval will be measured at time points before, during and after treatment, and maximum doses of JBT-101 to be tested in this study will not exceed 40 mg/day (given as 20 mg b.i.d.). In the JBT101-SSc-001 study, assessment of ECGs and corrected QT intervals using standard techniques revealed no clinically significant prolongation of corrected QT intervals or other significant electrocardiogram findings.

Studies of human reproduction have not been performed with JBT-101. It is not known if JBT-101 can cause fetal harm when administered to pregnant women or if it can negatively affect reproductive capacity. Women of childbearing potential should avoid becoming pregnant and should not be breastfeeding at the start of the study, during the study, and for 28 days after the last dose of study drug.

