6.1.7 Electrocardiograms and QT/QTc Intervals

Twelve-lead ECGs are to be recorded in triplicate at Screening and Visits 1 (Day 1) and 5 (Day 85). They will be evaluated for medically significant abnormalities and QT/QTc intervals. The QT/QTc intervals will be measured at Visit 1 (Day 1) before administration and between 2.5 and 3.5 hours after administration of study product in the clinic, at the time of maximum JBT-101 concentration in the blood.

The triplet twelve-lead ECGs are to be recorded at least 5 minutes apart, with the subject in a rested supine position for at least 10 minutes. Food and drink should not be consumed by the

subject within the 30 minutes before the ECGs are to be recorded. A central reading center will be used to read all ECGs and determine QT/QTc intervals.

Abnormal ECG findings will be reported as adverse events if they meet grading and reporting criteria (See Section 7.4, *Grading and Attribution of Adverse Events*).

6.1.8 **ARCI-M Questionnaire**

The ARCI-M questionnaire will be completed by subjects at Visits 1 (Day 1), 3 (Day 29), and 5 (Day 85). This is a 12-item yes-no questionnaire developed by the National Institute on Drug Abuse, designed to detect the full range of subjective responses experienced by marijuana users [106]. The ARCI-M questionnaire has been validated by subjects following marijuana smoking. The subject will be asked to fill out the ARCI-M questionnaire prior to other interactions with study staff except for Visit 1 (Day 1). At Visit 1 (Day 1), the ARCI-M questionnaire will be completed at the beginning of the visit, prior to interaction with study staff and between 2.5 and 3.5 hours after administration of study product in the clinic, at the time of maximum JBT-101 concentration in the blood. Evidence of psychotropic effects of the study drug in subjects will be identified by an increase of ≥ 1 in the ARCI-M score assessed longitudinally.

6.1.9 **Pregnancies**

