8.3.3 Safety Analyses

8.3.3.1 Adverse events

Safety will be assessed primarily by summarizing TEAEs, including treatment-emergent SAEs, and the proportion of subjects with TEAEs and treatment-emergent SAEs in each individual JBT-101 cohort (Cohort 1, Cohort 2, and Cohort 3) to the placebo (Cohort 4).

For placebo and each JBT-101 cohort, the frequency of AEs and SAEs from Screening through Visit 6 (Day 113) will be summarized by system organ class, preferred term, severity (grade), and relationship to study treatment.

Safety endpoint identified in Section 3.2.3, *Safety Endpoints*, will be summarized and listed separately. With the exception of the "psychotropic activity" endpoint, safety endpoints are "events". For each such endpoint, the number of events and numbers and percentages of subjects who experience these events will be summarized for placebo and each individual JBT-101 cohort. No formal statistical testing will be performed to compare safety in different cohorts.

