8.3.3.4 ARCI-M questionnaire

ARCI-M questionnaire scores will be summarized by visit for Visits 1 (Day 1) (before and after first dose of study drug), 3 (Day 29), and 5 (Day 85), and for change from Visit 1 (Day 1) prior to the first dose of study drug to the visit using continuous summary statistics. The number of subjects with an increase in score by ≥ 1 from Visit 1 (Day 1) prior to study product administration will be presented by visit for Visit 1 (Day 1) after study drug administration, Visits 3 (Day 29) and 5 (Day 85).

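### The ARCI-M is said to confirm that JBT-101 lacks psychotropic properties, but the planned analysis is descriptive only and cannot support a conclusion of absence

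*Protocol*

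**What the plan says.** Two background sections of the protocol state what the ARCI-M will deliver. Section 1.6 (Rationale for the Study): "Confirmation of the lack of psychotropic properties of oral JBT-101 will be done using the Addiction Research Center Inventory-Marijuana" questionnaire. Section 1.5.1 (Potential Risks): "Psychotropic activity of JBT-101 will be tested formally with the ARCI-M questionnaire".

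The working sections say less. Section 3.2.3 lists psychotropic activity, measured by ARCI-M, as safety endpoint 7. Section 6.1.8 describes the instrument ("This is a 12-item yes-no questionnaire") and says evidence of a psychotropic effect in subjects "will be identified by an increase of ≥ 1 in the ARCI-M score assessed longitudinally". Section 8.3.3.4 summarises the score by visit, and its change from the value "prior to the first dose of study drug to the visit using continuous summary statistics". It adds: "The number of subjects with an increase in score by ≥ 1 from Visit 1 (Day 1) prior to study product administration will be presented", broken down per visit. Section 8.3.3.1 closes the safety comparisons: "No formal statistical testing will be performed to compare safety in different cohorts".

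Section 8.3 tabulates summaries by treatment group. Section 8.1 sizes the trial on the pain NRS alone, at about 25 subjects per arm.

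**The concern.** Confirming that a property is lacking is a claim of no effect. It needs a statement of how large an effect would still count as none, and an interval or bound showing that anything larger has been excluded. The protocol has neither for the ARCI-M. It also promises a formal test in one place and excludes formal safety comparisons in another.

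Limited psychoactivity is part of the protocol's safety case for this cannabinoid-derived drug (section 1.2.2), and the data are to inform the benefit-risk decision on pivotal testing (section 1.6). The question is not closed. Section 1.5.1 speaks of little evidence of psychotropic activity, not none. Section 1.3.4 reports two withdrawals in the cystic fibrosis trial judged related to JBT-101, one for reduced cognitive clarity and one for feeling unmotivated; one placebo subject there also withdrew with cognitive complaints. If the arms merely look alike in a table, a report that follows section 1.6 could present that as confirmed absence.

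**Working it through.** **1. Is there any rule that could establish absence?**

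- Formal test: promised in 1.5.1, excluded by 8.3.3.1.
- Between-arm limit: none stated.
- Confidence bound on a difference from placebo: none stated in 8.3.3.4.
- Threshold: a rise of at least 1 point (6.1.8, 8.3.3.4). It classifies a subject. Nothing says how many such subjects, or what excess over placebo, would contradict a lack of effect.

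**2. The plan's own figure.** The protocol gives no power or precision figure for the ARCI-M. Its stated power is for the 3 df pain test: above 80% with two effective doses, a 1.6-point effect and 25 per group. As a check on that design:

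- Sxx for 84 daily scores = 84 × (84² − 1)/12 = 49,385.
- Variance of the 84-day change = (0.00063 + 0.49/49,385) × 84² = 4.515.
- Group changes 0, −0.4, −1.6, −1.6 have mean −0.9 and squared deviations summing to 0.81 + 0.25 + 0.49 + 0.49 = 2.04.
- Noncentrality = 25 × 2.04/4.515 = 11.3.
- Power = 79.8% with 96 denominator df and 81.5% with large denominator df.

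The pain figure reproduces, but it says nothing about the ARCI-M.

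**3. Precision that 25 per arm would give.** The protocol states no ARCI-M SD, so results are in SD units.

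- One dose versus placebo: 95% half-width = t(0.975, 48) × √(1/25 + 1/25) = 2.011 × 0.283 = 0.57 SD.
- Three doses pooled versus placebo: 1.984 × √(1/75 + 1/25) = 1.984 × 0.231 = 0.46 SD.

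**4. What a zero count would exclude** (one-sided 95%, 1 − 0.05^(1/n)):

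- 0 of 25: 1 − 0.05^(1/25) = 11.3%.
- 0 of 75: 1 − 0.05^(1/75) = 3.9%.

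**5. Sensitivity of a comparison, if one were made.** The test and the effect sizes here are assumptions: a two-sided 5% two-sample t-test, with power from the noncentral t distribution.

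| Assumed shift | Miss rate, one dose vs placebo (25 vs 25) |
|---|---|
| 0.3 SD | 82% |
| 0.4 SD | 72% |
| 0.5 SD | 59% |
| 0.6 SD | 45% |
| 0.8 SD | 21% |
| 1.0 SD | 7% |

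At 0.5 SD the miss rate is 43% with the doses pooled (75 vs 25) and 63% with 22 per arm.

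**6. What an explicit limit would need.** If the true difference is zero, the smallest limit that 25 per arm could exclude with 80% power (one-sided 2.5%, normal approximation) is (1.96 + 0.84) × √(2/25) = 0.79 SD. Excluding 0.5 SD with 80% power needs 63 per arm.

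**The case against.** The strongest reply is that the confirmation sentence is rationale prose, not a planned inference. The objective is to evaluate safety and tolerability, section 6.1.8 looks for evidence of an effect, and no analysis section has a rule for declaring psychoactivity absent. Confirmation may simply mean corroborating earlier data: section 1.3.4 reports no psychoactivity on formal testing up to 80 mg daily, and ARCI-M changes similar to placebo in the cystic fibrosis trial. Nor does the ARCI-M stand alone. Cannabinoid-type adverse events are monitored, PROMIS Cognitive Function is collected, and two similar Grade 3 or higher events associated with CB1 agonists, at least possibly related, trigger an emergency DSMB review. Descriptive safety analysis is ordinary in a 100-subject Phase 2 trial, and interval detail may sit in a statistical analysis plan that is not shown.

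Much of this stands. The descriptive analysis is not itself a fault, drug and placebo will appear side by side, and the endpoint has a subject-level definition. What does not go away is that the protocol states a conclusion and a formal test that its own analysis sections do not provide. A statistical analysis plan that follows 8.3.3.1 and 8.3.3.4 as written would not cure that.

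A reader might also infer that the trial would probably miss a relevant psychotropic effect, taking 59% as its error rate. The documents do not support this. No such test is planned, nothing in the protocol makes 0.5 SD the relevant shift, and the figure runs from 82% to 7% over 0.3 to 1.0 SD. With the doses pooled, a 0.5 SD shift is missed less often than it is found (43%).

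**Conclusion.** The point holds as a mismatch between the stated aim and the planned analysis. Sections 1.6 and 1.5.1 promise confirmation and formal testing; sections 8.3.3.1 and 8.3.3.4 deliver description only. No conclusion of absence can be drawn from that analysis whatever effect size is assumed, because no between-arm bound is planned.

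On size, intervals from this trial would be about 0.57 SD wide on each side per dose. A zero count in one arm would leave true rates up to 11% open (3.9% pooled). These figures assume 25 evaluable subjects per arm and, for the means, a common SD and approximate normality of a 12-item score. The miss rates in the table are illustrations under assumed effects. They are not properties of a planned test. The primary efficacy analysis is not affected.

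**What to change.** - **Section 8.3.3.4:** for each dose and for pooled JBT-101, report the difference from placebo with a 95% confidence interval in mean ARCI-M change and in the proportion of subjects with a rise of at least 1.
- **Section 1.6:** recast the aim as *estimation of* psychotropic properties in place of confirming that they are lacking.
- **Section 1.5.1:** bring the statement about formal testing into line with 8.3.3.1.
- **If a claim of absence is wanted:** fix an upper limit before unblinding and make the claim only if the upper confidence bound falls below it. At 25 per arm only a wide limit is realistic, about 0.79 SD for 80% power per dose.

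The cost is a few words and one extra table, with no new data, visits or subjects. The downside is that the study may have to report that absence of a psychotropic effect was not established.
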